## 4. Study Objectives

### 4.1. Primary Objective

The primary objective of this study is to test the hypothesis that baricitinib 4-mg once daily (QD) plus topical corticosteroids (TCS) or baricitinib 2-mg QD plus TCS is superior to placebo plus TCS in the treatment of patients with moderate-to-severe atopic dermatitis (AD), as assessed by the proportion of patients achieving 75% improvement from baseline using the Eczema Area and Severity Index score (EASI75) at Week 16.

In particular, the associated estimand for this objective is to measure the effect of therapy with baricitinib as assessed by the proportion of patients with a response of EASI75 at Week 16 assuming treatment response disappears after patients are rescued or discontinued from the study or treatment. See Sections 6.3 and 6.10 for details on how this estimand handles outcomes after the occurrence of any intercurrent event through nonresponder imputation (NRI).

### 4.2. Secondary Objectives

#### 4.2.1. Key Secondary Objectives

Key Secondary These are prespecified objectives that will be adjusted for multiplicity	
Objectives	Endpoints
To test the hypothesis that baricitinib 1-mg + TCS is superior to placebo + TCS in the treatment of patients with moderate-to-severe AD	
 
Proportion of patients achieving EASI75 at 16 weeks
 

To compare the efficacy of baricitinib 4-mg + TCS, baricitinib 2-mg + TCS, or baricitinib 1-mg + TCS to placebo + TCS in AD during the double-blind placebo-controlled treatment period as measured by improvement of signs and symptoms of AD	
 
Proportion of patients achieving IGA of 0 or 1 with a <math>\geq 2</math>-point improvement at 16 weeks
 
Proportion of patients achieving EASI90 at 16 weeks
 
Percent change from baseline in EASI score at 16 weeks
 
Proportion of patients achieving SCORAD75 at 16 weeks
 

To compare the efficacy of baricitinib 4-mg + TCS, baricitinib 2-mg + TCS, or baricitinib 1-mg + TCS to placebo + TCS in AD during the double-blind placebo-controlled treatment period as assessed by patient-reported outcome measures	
 
Proportion of patients achieving a 4-point improvement in Itch NRS at 16 weeks, 4 weeks, 2 weeks, and 1 week
 
Mean change from baseline in the score of Item 2 of the ADSS at 16 weeks and 1 week
 
Mean change from baseline in Skin Pain NRS at 16 weeks
 

To compare the efficacy of baricitinib 4-mg + TCS, baricitinib 2-mg + TCS, or baricitinib 1-mg + TCS to placebo + TCS in AD during the double-blind placebo-controlled treatment period as measured by improvement of signs and symptoms of AD	
 
Proportion of patients achieving IGA of 0 or 1 with a <math>\geq 2</math>-point improvement from baseline at 24 weeks
 
Proportion of patients achieving EASI75 at 24 weeks
 

**Key Secondary Objectives**

Abbreviations: AD = atopic dermatitis; ADSS = Atopic Dermatitis Sleep Scale; EASI75 = 75% improvement from baseline in Eczema Area and Severity Index score; EASI90; 90% improvement from baseline in Eczema Area and Severity Index score; IGA = Investigator's Global Assessment for AD; NRS = Numeric Rating Scale; SCORAD75 = 75% decrease from baseline in Scoring Atopic Dermatitis values; TCS = topical corticosteroids.

**4.2.2. Other Secondary Objectives**

Other Secondary These are prespecified objectives that will not be adjusted for multiplicity	
Objectives	Endpoints
To test the hypothesis that baricitinib 4-mg + TCS, baricitinib 2-mg + TCS, or baricitinib 1-mg + TCS is superior to placebo + TCS in the treatment of moderate-to-severe AD	
 
Proportion of patients achieving IGA of 0 or 1 with a <math>\geq 2</math>-point improvement at Week 4 and Week 52
 
Proportion of patients achieving EASI75 at Week 4 and Week 52
 

To compare the efficacy of baricitinib 4-mg + TCS, baricitinib 2-mg + TCS, or baricitinib 1-mg + TCS to placebo + TCS in AD during the double-blind placebo-controlled treatment period as measured by improvement in signs and symptoms of AD	
 
Proportion of patients achieving EASI50 at 16 weeks
 
Proportion of patients achieving IGA of 0 at 16 weeks
 
Mean change from baseline in SCORAD at 16 weeks
 
Proportion of patients achieving SCORAD90 at 16 weeks
 
Mean change from baseline in BSA affected at 16 weeks
 
Proportion of patients developing skin infections requiring antibiotic treatment by Week 16
 
Mean number of days without use of background TCS over 16 weeks
 
Mean gram quantity of background TCS used over 16 weeks (tube weights)
 

To compare the efficacy of baricitinib 4-mg + TCS, baricitinib 2-mg + TCS, or baricitinib 1-mg + TCS to placebo + TCS in AD during the double-blind placebo-controlled treatment period as assessed by patient-reported outcome measures	
 
Percent change from baseline in Itch NRS at Week 52, Week 24, Week 16, Week 4, and Week 1
 
Proportion of patients achieving a 4-point improvement in Itch NRS at 24 weeks
 
Mean change from baseline in the total score of the POEM at 16 weeks
 
Mean change from baseline in the PGI-S-AD scores at 16 weeks
 
Mean change from baseline in HADS total scores at 16 weeks
 
Mean change from baseline in the DLQI total scores at 16 weeks
 
Mean change from baseline in the WPAI-AD total scores at 16 weeks
 
Mean change from baseline in the EQ-5D-5L total scores at 16 weeks
 

Substudy: Randomized Downtitration These are prespecified objectives that will be not be adjusted for multiplicity	
All Patients Entering the Substudy To evaluate the change in clinical response after treatment downtitration from baricitinib	
 
• 4-mg to 2-mg compared with patients who are rerandomized to remain on baricitinib 4-mg
 
• 2-mg to 1-mg compared with patients randomized to remain on baricitinib 2-mg
 

Patients Entering the Substudy with IGA 0 or 1 To evaluate the change in clinical response after treatment downtitration from baricitinib	
 
• 4-mg to 2-mg compared with patients who are rerandomized to remain on baricitinib 4-mg
 
• 2-mg to 1-mg compared with patients randomized to remain on baricitinib 2-mg
 

Patients Retreated during Substudy To evaluate the ability to recapture efficacy based on clinical measures after experiencing a loss of treatment benefit:	
 
• Proportion of patients with a response of IGA 0, 1, or 2 within 16 weeks of retreatment
 
• Proportion of patients with a response of IGA 0 or 1 within 16 weeks of retreatment
 
• Proportion of patients with a response of EASI75 from baseline of originating study within 16 weeks of retreatment
 

Patients Not Entered into Substudy These are prespecified objectives that will not be adjusted for multiplicity	
All Patients To evaluate the long-term effect of baricitinib dose on clinical measures	
 
• Proportion of patients with a response of IGA 0, 1, or 2 assessed at Weeks 68 and 104
 
• Proportion of patients with a response of IGA 0 or 1 assessed at Weeks 68 and 104
 
• Proportion of patients with a response of EASI75 assessed at Weeks 68 and 104
 

Patients with IGA 0 or 1 To evaluate the long-term effect of baricitinib dose on clinical measures	
Non-responder Patients at Week 52	

Abbreviations: AD = atopic dermatitis; ADSS = Atopic Dermatitis Sleep Scale; BSA = body surface area; DBL = database lock; DLQI = Dermatology Life Quality Index; EASI75 = 75% improvement from baseline in Eczema Area and Severity Index score; EQ-5D-5L = the European Quality of Life-5 Dimensions 5 Levels; HADS = Hospital Anxiety Depression Scale; IGA = Investigator's Global Assessment for AD; NRS = Numeric Rating Scale; PGI-S-AD = Patient Global Impression of Severity-Atopic Dermatitis; POEM = Patient-Oriented Eczema Measure; SCORAD90 = 90% decrease from baseline in Scoring Atopic Dermatitis values; WPAI-AD = Work Productivity and Activity Impairment-Atopic Dermatitis; TCS = topical corticosteroids.

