5.1.3. Period 3: Double-Blind, Long-Term Extension

Patients who complete the study through Week 52 will progress into the double-blind long-term extension phase through Week 104 (Visit 22). Daily diary collection will continue through Week 68 (Visit 18) of Period 3.

Concomitant use of background TCS therapy will continue during this treatment period as described in Section 7.7.2.

5.1.3.1. Randomized Downtitration Substudy at Week 52

At Week 52, all patients will be evaluated for substudy eligibility. To be eligible, a patient must meet all of the following criteria:

- have an IGA 0, 1 (Responder) or 2 (Partial responder) at Week 52
- have not used high- or ultra-high potency TCS in the last 14 days (potency classification in [Appendix 7](#))
- do not currently have study drug interrupted
- have been assigned to baricitinib 2-mg or 4-mg at baseline (assessed by interactive web-response system [IWRS])

Treatment

Treatment in the substudy is illustrated in [Figure JAIN.1](#). Patients eligible for the substudy will be rerandomized at a 1:1 ratio at Week 52 based on the baricitinib treatment group assigned at baseline:

- 4-mg QD rerandomized to baricitinib 4-mg QD, or baricitinib 2-mg QD
- 2-mg QD rerandomized to baricitinib 2-mg QD, or baricitinib 1-mg QD

Note: Intensification of emollients and TCS may be continued or initiated to control worsening and unacceptable symptoms of AD any time during this treatment period. For management of TCS, follow the guidelines in [Section 7.7.2](#).

Retreatment

During the substudy, if worsening of AD symptoms occurs such that IGA increases to ≥ 3 , the patient will be automatically retreated with their presubstudy baricitinib dose. When the IGA is ≥ 3 , the investigator should reinstate background TCS therapy (e.g., triamcinolone 0.1% cream and/or hydrocortisone 2.5% ointment), provided the patients are not currently using TCS, and may prescribe high- or ultra-high-potency TCS following the guidelines for use of Rescue Therapies ([Section 7.7.5](#) [Rescue Therapy]). An unscheduled visit may be needed to assess worsening of symptoms and to perform clinical safety and efficacy assessments immediately before retreatment.

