#### *Period 3 and Period 4 (Study Weeks 52 to 200)*

For analysis of endpoints assessed at scheduled visits in Periods 3 and 4, baseline from Week 0 will be used for categorical endpoints, such as EASI75, Itch NRS  $\geq 4$ -point improvement response, etc. Baseline from Week 0 will also be used for EASI-related, continuous endpoints, such as EASI change or percent change from baseline. For the other continuous endpoints such as Itch NRS and Dermatology Life Quality Index (DLQI) change from baseline, the analysis will be done using the Week 52 baseline. The methodology for defining Week 52 as the baseline is the same as the methodology for defining Week 0 of the originating study described above, anchoring on the first study drug administration of Period 3. See [Table JAIN.6.9](#) and [Table JAIN.6.12](#) for a detailed descriptions on endpoint derivation and associated baseline definition.

Baseline daily-diary definition will be same to the Period 2's definition for daily-diary data.

Postbaseline measurements are collected after study drug administration through Week 200 (Visit 28) or early discontinuation visit. Data collected on scheduled visits will generally be used for efficacy and health outcome analyses. If data for a scheduled visit are missing, data from the most proximal unscheduled visits, if available, will be used if it falls within visit windows as follows: a 2-day interval around the scheduled visit day (4-day window) is applied to Visits 3 to 6 (Week 1, 2, 4, 8), a 4-day interval around the scheduled visit day (8-day window) is applied to Visits 7 to 9 (Week 12, 16, 20), a 5-day interval around the scheduled visit day (10-day window) is applied to Visits 10 to 14 (Week 24, 32, 40, 48, 52), a 4-day interval around the scheduled visit day (8-day window) is applied to Visits 15 to 18 (Week 56, 60, 64, 68), a 5-day interval around the scheduled visit day (10-day window) is applied to Visits 19 to 22 (Week 76, 84, 92, 104), and a 7-day interval around the scheduled visit day (14-day window) is applied to

Visits 23 to 28 (Week 120, 136, 152, 168, 184, and 200). If there is more than 1 unscheduled visit within the defined visit window and no scheduled visit is available, the unscheduled visit closest to the scheduled visit date will be used. If only 2 equal distance unscheduled visits are available, the later of the 2 visits will be used.

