**Table JAIN.6.9. Description of Primary, Secondary, and Exploratory Efficacy Analyses (Period 3 and Period 4)**

Measure	Variable	Population (Section 6.2.1)	Analysis Method (Section 6.2.2)	Time Point	Baseline definition
Validated Investigator's Global Assessment for AD (IGA)	Proportion of patients with a response of IGA 0 or 1	LTE Substudy Population	Descriptive using Obs and mLOCF	Weeks 52-200	N.A.
		LTE Substudy Population – Patients with IGA of 0 or 1 at Week 52	Descriptive using Obs and mLOCF	Weeks 52-200	
		LTE Non-responder Population	Descriptive using Obs and mLOCF	Weeks 52-200	
	Proportion of patients with a response of IGA 0, 1, or 2	LTE Responder & Partial Responders who did not enter the substudy	Descriptive using Obs and mLOCF	Weeks 52-200	
	Time to relapse (time to IGA $\geq 3$ )	LTE Substudy Relapse Population	
 
Descriptive
 
Kaplan-Meier plot
 
	Downtitration and withdrawal period	N.A.
	Proportion of patients with a response of IGA(0, 1), IGA(0, 1, 2) within 16 weeks of Disease Retreatment	LTE Substudy Relapse Population	Descriptive	Downtitration and withdrawal period	N.A.
Eczema Area and Severity Index (EASI)	Proportion of patients achieving EASI75 (achieving EASI percent change from baseline $\leq -75$ )	LTE Substudy Population	Descriptive using Obs and mLOCF	Weeks 52-200	Week 0 Baseline
		LTE Substudy Population - Patients with IGA of 0 or 1 at Week 52	Descriptive using Obs and mLOCF	Weeks 52-200	Week 0 Baseline
		LTE Non-responder Population	Descriptive using Obs and mLOCF	Weeks 52-200	Week 0 Baseline

Measure	Variable	Population (Section 6.2.1)	Analysis Method (Section 6.2.2)	Time Point	Baseline definition
	Proportion of patients achieving EASI50	LTE Responder & Partial Responders who did not enter the substudy	Descriptive using Obs and mLOCF	Weeks 52-200	Week 0 Baseline
	Proportion of patients achieving EASI90				
Eczema Area and Severity Index (EASI)	Change from baseline in EASI score	LTE Substudy Population	Descriptive using Obs and mLOCF	Weeks 52-200	Week 0 Baseline
	Percent change from baseline in EASI score	LTE Substudy Population – Patients with IGA of 0 or 1 at Week 52	Descriptive using Obs and mLOCF	Weeks 52-200	Week 0 Baseline
		LTE Non-responder Population	Descriptive using Obs and mLOCF	Weeks 52-200	Week 0 Baseline
		LTE Responder & Partial Responders who did not enter the substudy	Descriptive using Obs and mLOCF	Weeks 52-200	Week 0 Baseline

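### Recapture of response after retreatment is counted over a 16-week window holding anything from 3 scheduled looks to none, so the descriptive rates by dose sequence are not like for like

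*SAP*

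**What the plan says.** SAP 4.2.2, under patients retreated during the substudy, lists "Proportion of patients with a response of IGA 0, 1, or 2 within 16 weeks of retreatment" and the matching IGA 0 or 1 and EASI75 proportions. Table JAIN.6.9 repeats the IGA versions as "Proportion of patients with a response of IGA(0, 1), IGA(0, 1, 2) within 16 weeks of Disease Retreatment", for the LTE Substudy Relapse Population, with the method given only as descriptive. Neither place names a visit, a minimum number of assessments, or a rule for a patient with none. The neighbouring extension endpoints name fixed weeks (68 and 104).

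Substudy entry requires patients to "have an IGA 0, 1 (Responder) or 2 (Partial responder) at Week 52" (Protocol 5.1.3.1), so the first scheduled visit at which relapse can be found is Week 56. Relapse is IGA of 3 or more and triggers retreatment at any time in Periods 3 and 4 (Protocol 5.1.3.1 and 5.1.4).

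The visits (Protocol Table JAIN.1; SAP 6.2.2.1) are at Weeks 56, 60, 64 and 68 (±4 days), Weeks 76, 84, 92 and 104 (±5 days), then every 16 weeks from 120 to 200 (±7 days). Table JAIN.6.3 sets out the relapse population by dose sequence: 4/4/4, 4/2/4, 2/2/2 and 2/1/2.

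**The concern.** A proportion defined as responding at some point in a window depends on how often, and how late in that window, the patient is examined. Here both are set by the calendar week of relapse. Time to relapse is itself something the substudy describes by arm, so arms may well differ in it. Two arms with the same true recovery after retreatment could then show different recapture rates, and a reader would have no means of separating schedule from drug. Whether a lost response returns is central to interpreting down-titration, which makes the column-by-column reading likely even though no test is planned.

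**Working it through.** The documents give no sample size, expected rate or stated figure for this endpoint, so there is nothing to reproduce. The check has four steps.

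**1. Count the looks.** For retreatment at scheduled week w, count scheduled visits v with w < v ≤ w + 16.

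| Retreatment week | Looks | Weeks after retreatment |
|---|---|---|
| 56 | 3 | 4, 8, 12 |
| 60 | 3 | 4, 8, 16 |
| 64 | 2 | 4, 12 |
| 68, 76 | 2 | 8, 16 |
| 84 | 1 | 8 |
| 92 | 1 | 12 |
| 104, 120, 136, 152, 168, 184 | 1 | 16 |
| 200 | 0 | none |

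Retreatment at an unscheduled visit shifts these counts: before Week 56 there are 4 looks; at about Weeks 88 to 91.5 there are 2.

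**2. If response fluctuates between visits, the number of looks matters.** Let p be the chance of response at one look (assumed; not in the documents). With independent looks, P(any) = 1 − (1 − p)^k. At p = 0.3 and k = 3 this is 1 − 0.7³ = 65.7%, against 30.0% for k = 1. Independence is an extreme. With an exchangeable probit model of latent correlation ρ, P(any) = 1 − E[(1 − Φ((c + √ρ·U)/√(1 − ρ)))^k], where c = Φ⁻¹(p) and U is standard normal. For ρ from 0.85 down to 0.5:

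| p | 1 look | 2 looks | 3 looks |
|---|---|---|---|
| 0.3 | 30% | 38–44% | 42–53% |
| 0.5 | 50% | 59–67% | 63–75% |

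As an arm-level illustration, suppose one arm relapses early (70/20/10% of patients with 3/2/1 looks) and another late (30/30/40%); both mixes are assumed. At p = 0.3 and ρ = 0.5 (53.0, 44.3 and 30.0%), the early arm shows 0.7×53.0 + 0.2×44.3 + 0.1×30.0 = 49.0% and the late arm 0.3×53.0 + 0.3×44.3 + 0.4×30.0 = 41.2%. That is a gap of about 8 points with no true difference. At ρ = 0.85 (41.9, 37.7 and 30.0%) the figures are 39.9% and 35.9%, a gap of 4 points.

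**3. If response is durable once regained, the time of the last look matters.** Assume exponential time to recapture with 60% recaptured by 16 weeks, so F(t) = 1 − 0.4^(t/16). A last look at 8 weeks (retreatment at Week 84) shows 1 − 0.4^0.5 = 36.8%. At 12 weeks (Weeks 56, 64, 92) it shows 1 − 0.4^0.75 = 49.7%. At 16 weeks (Weeks 60, 68, 76 and 104 to 184) it shows 60.0%. The patient retreated at Week 56 now does worse than the one retreated at Week 104, despite having three looks to one.

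**4. The edge of the window.** From Week 104 the only look falls at nominal day 112. Suppose 16 weeks is applied as a strict 112 days, and let i and j be the deviations in days of the retreatment visit and the next visit. The look is lost when j > i. From Week 104 (±5) to Week 120 (±7), 77 of 11 × 15 = 165 combinations have j > i, or 46.7%. Between Period 4 visits (±7, ±7) it is 105 of 225, again 46.7%. This treats every day within tolerance as equally likely, which is an assumption. Under the same cutoff, a late visit can also cut Week 60 to 2 looks and Weeks 68 and 76 to 1.

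**The case against.** The strongest reply is that no comparison of recapture is planned. The retreatment row speaks of evaluating recapture; the down-titration rows are the ones that compare arms. SAP 6.2.2.3 rules out inferential tests in Periods 3 and 4, SAP 6.2.2 calls efficacy after Week 104 exploratory, and the endpoint is absent from the protocol's substudy objectives. Relapsers are also selected after randomisation, and the 4/4/4 and 2/2/2 groups are retreated at an unchanged dose, so the columns would not be strictly comparable even with equal looks. All of that stands and limits the weight of the point. It does not remove it: the rates will be set side by side by sequence, and unequal looks add a further, avoidable difference.

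A reader might go further and infer that the endpoint favours arms that relapse early, and so flatters the reversibility of down-titration. The documents do not support that: step 3 shows the direction can reverse, and neither per-visit response nor relapse timing by arm is given. A reader might also infer that late relapsers with a slightly late visit cannot be scored as recaptured. That needs a strict day-112 cutoff, which the SAP does not state; its visit windows are organised around nominal weeks.

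Unscheduled visits could in principle add looks. SAP 6.2.2.1 brings them in only when a scheduled visit is missing, while SAP 6.2 keeps them for some categorical analyses. Either way they do not equalise the looks.

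**Conclusion.** The point holds as one of comparability. The look counts follow directly from the schedule and need no assumption beyond reading the endpoint as any response in the window: 3, 2, 1 or 0 looks, with the last at 8, 12 or 16 weeks for retreatment at a scheduled visit. Nothing in the SAP equalises or displays this. The size is not known. Under the assumed fluctuating model a patient's rate rises by roughly 12 to 25 points from one look to three; under the assumed durable model the spread is about 23 points (36.8% to 60.0%) and follows timing instead. The 47% loss of Period 4 looks is conditional on a strict cutoff and uniform visit days. Type I error and the primary and key secondary results are untouched. This should be corrected before the recapture rates are interpreted, but it is not critical to the trial.

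**What to change.** Amend SAP 4.2.2 and the retreatment row of Table JAIN.6.9 as follows.

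1. Assign looks by nominal visit week, so that the scheduled visit nominally 16 weeks after retreatment counts when it occurs within its protocol window.
2. Keep the any-visit proportion, but tabulate it by retreatment visit and by number of scheduled looks. Show retreatment at unscheduled visits separately.
3. Beside it, report a one-look proportion at the last scheduled visit nominally no more than 16 weeks after retreatment, with the weeks from retreatment shown. Timing still varies: 8 to 16 weeks for scheduled retreatment, and less for some off-schedule cases (retreatment at Week 118 leaves only Week 120).
4. Exclude from the denominator, and count separately, patients with no scheduled visit in the window before the lock, such as those retreated at Week 200.

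Forcing a single visit nearest to 16 weeks within 12 to 20 weeks looks tidier but works less well. If ties go to the later visit, retreatment at Weeks 56, 64 and 84 is scored at 20 weeks, outside the endpoint, and many off-schedule retreatments have no such visit.

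The same edit should exempt this endpoint from the LTE Substudy censoring rule in SAP 6.3, which read literally removes results after retreatment.

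The cost is SAP wording and one extra descriptive table, with no new visits or data. Cells will be small, and the one-look rate will be somewhat lower than the any-visit rate. SAP Version 5 postdates the Week 104 lock and individual unblinding has occurred since, so the change should be documented as an addition to the existing definition.

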## 4.3. Exploratory Objectives

The exploratory objectives of this study are as follows:

Objectives/Endpoints

Exploratory Endpoints may include evaluating the response to baricitinib treatment regimens on clinical measures and patient-reported outcomes. These endpoints may include dichotomous endpoints or change from baseline for the following measures: IGA, EASI, SCORAD, POEM, DLQI, WPAI-AD, EQ-5D-5L, Itch NRS, ADSS Item 1, 2, and 3 scores, Skin Pain NRS, SF-36, and PGI-S-AD. Patients continuing on placebo as responders will be assessed during the Long-Term Extension for relevant efficacy endpoints.

Prior to the WK104 DBL, exploratory analysis endpoints include:

EASI at Week 16:
 
 
• Proportion of patients achieving EASI <math>\leq 7</math>
 
• Change from baseline in EASI total score
 

EASI at Week 52:
 
 
• Proportion of patients achieving EASI50
 
• Proportion of patients achieving EASI90
 
• Change and percent change from baseline in EASI total score
 
• Proportion of patients achieving EASI <math>\leq 7</math>
 

Proportions of patients achieving IGA of 0 or 1 or 2 at Week 52

SCORAD at Week 16:
 
 
• Proportion of patients achieving SCORAD <math>\leq 25</math> (in the subset of patients with SCORAD <math>>25</math> at baseline)
 
• Percent change from baseline in SCORAD
 

SCORAD at Week 52:
 
 
• Proportion of patients achieving SCORAD75
 
• Mean change and percent change from baseline in SCORAD
 
• Proportion of patients achieving SCORAD <math>\leq 25</math> (in the subset of patients with SCORAD <math>>25</math> at baseline)
 

To evaluate the effect of maintaining baricitinib effect on key clinical measures:
 
 
• Proportion of IGA (0,1) responders at Week 24 for those patients with an IGA (0,1) response at Week 16
 
• Proportion of EASI75 responders at Week 24 for those patients with an EASI75 response at Week 24
 

Time to event analysis:
 
 
• Time to first EASI75 reduction response
 
• Time to first IGA (0,1) response
 
• Time to first Itch NRS 4-point improvement response
 


ADSS at Week 16:
 
 
• Mean change from baseline in ADSS Item 1 score at Week 1 and Week 16
 
• Mean change from baseline in ADSS Item 3 ADSS at Week 1 and Week 16
 
• Proportion of patients achieving a <math>\geq 1</math>-point improvement in ADSS Item 1 score for those with a baseline Item 1 score <math>\geq 1</math>
 
• Proportion of patients achieving a <math>\geq 2</math>-point improvement in ADSS Item 2 score for those with a baseline Item 2 score <math>\geq 2</math>
 
• Proportion of patients achieving a 1-point improvement in ADSS Item 3 score for those with a baseline Item 3 score <math>\geq 1</math>
 
• Proportion of patients achieving a <math>\geq 1.5</math>-point improvement in ADSS Item 2 score for those with a baseline Item 2 score <math>\geq 1.5</math>
 

ADSS Item 2 at Week 52:
 
 
• Mean change from baseline in ADSS Item 2 score
 

Skin Pain at Week 16:

- Proportion of patients achieving a  $\geq 4$ -point improvement for those with a baseline Skin Pain NRS score  $\geq 4$

Skin Pain NRS at Week 52:

- Mean change from baseline in Skin Pain NRS
- Proportion of patients achieving a  $\geq 4$ -point improvement for those with a baseline Skin Pain NRS score  $\geq 4$

DLQI at Week 16:

- Proportion of patients achieving a  $\geq 4$ -point improvement in DLQI total score for those with a baseline DLQI total score  $\geq 4$
- Proportion of patients achieving a DLQI total score of 5 or less for those with a baseline DLQI total score  $> 5$
- Proportion of patients achieving DLQI total score of 0 or 1 for those with a baseline DLQI score  $> 1$

DLQI at Week 52:

- Proportion of patients achieving a  $\geq 4$ -point improvement in DLQI total score for those with a baseline DLQI total score  $\geq 4$
- Proportion of patients achieving a DLQI total score of 5 or less for those with a baseline DLQI total score  $> 5$
- Mean change from baseline in DLQI total score

POEM at Week 16:

- Proportion of patients achieving a  $\geq 4$ -point improvement in POEM total score for those with a baseline total score  $\geq 4$
- Proportion of patients achieving a  $\geq 3.4$ -point improvement in POEM total score for those with a baseline total score  $\geq 3.4$

POEM at Week 52:

- Mean change from baseline in the total score of the POEM at 16 weeks
- Proportion of patients achieving a  $\geq 4$ -point improvement in POEM total score for those with a baseline total score  $\geq 4$

HADS (including Week 52):

- Proportion of patients achieving a HADS Anxiety Score  $< 8$  for those with a baseline HADS Anxiety Score  $\geq 8$
- Proportion of patients achieving a HADS Depression Score  $< 8$  for those with a baseline HADS Depression Score  $\geq 8$
- Proportion of patients achieving improvement in HADS Anxiety Score or HADS Depression Score  $< 8$  for those with a baseline HADS Anxiety Score  $\geq 8$  or a baseline HADS Depression Score  $\geq 8$
- Change from baseline in HADS total score

BSA at Week 52:

- Mean change from baseline in BSA affected

Itch NRS at Week 52:

- Proportion of patients achieving a 4-point improvement in Itch NRS

Skin infections at Week 52:

- Proportion of patients developing skin infections requiring antibiotic treatment

Mean number of days without use of background TCS over 52 weeks

Mean gram quantity of background TCS used over 52 weeks (tube weights)

